6.3.2. Missing Data

For secondary efficacy analyses of ALP response rates, missing values will be considered as non-responders.

Additional sensitivity analysis will be performed using LOCF, and it will also be performed modifying the handling missing data for ALP response criteria. For the modified response criteria, all OCA treated subjects, missing data will be considered non-responders. For Placebo patients, missing data will be considered responders.

Otherwise, analysis will be done using observed data only; missing values will not be imputed.

6.3.3. Partial Dates

If only a partial date is available and is required for a calculation, the following standards will be applied:

- Diagnosis date (eg, PSC diagnosis date)
 - For missing day only: Day will be imputed as the first day of the month (ie, 01).
 - For missing day and month: Day and month will be imputed as the first day of the year (ie, 01 January).
- Start dates (eg, AE onset date or start date of medication)

- For missing start day only: Day will be imputed as the first day of the month (ie, 01) with the following exception: if the partial date falls in the same month and year as the date being used in the calculation (eg, first dose date, informed consent date), then the partial date will be imputed to equal the date being used for the calculation.
- For missing start day and month: Day and month will be imputed as the first day of the year (ie, 01 January) with the following exception: if the partial date falls in the same year as the date being used in the calculation (eg, first dose date, informed consent date), then the partial date will be imputed to equal the date being used for the calculation.
- Imputed start dates must be prior to the stop date.
- Stop dates (eg, AE resolution date or stop date of medication)
 - For missing stop day only: Day will be imputed as the last day of the month (ie, 28, 29, 30, or 31).
 - For missing stop day and month: Day and month will be imputed as the last day of the year (ie, 31 December).
 - Imputed dates should not extend beyond the DB phase (ie, date of completion or discontinuation of the DB phase).
 - Imputed stop dates must be on or after the start date.

6.3.4. Data Conventions

Unless otherwise specified, in summary tables of continuous variables, the minimum and maximum values will be displayed to the same number of decimal places as the raw data, the mean and median will be presented to one extra decimal place compared to the raw data, and the SD and SE of the mean will be displayed to two extra decimal places compared to the raw data. Rounding will only occur after all calculations have been incorporated. For tables where rounding is required, rounding will be done to the nearest round-off unit; for example, when rounding to the nearest integer, values \geq XX.5 will be rounded up to XX + 1 (eg, 97.5 will round up to 98), whereas values <XX.5 will be rounded down to XX (eg, 97.4 will round down to 97).

Percentages based on frequency counts will be based on available data, and denominators will generally exclude missing values unless some form of imputation is defined or a ‘missing’ category is presented. For frequency counts of categorical variables, categories with zero counts will be displayed for the sake of completeness. For example, if none of the subjects discontinue due to “lost to follow-up,” this reason will be included in the table with a count of 0.

Percentages based on frequency counts will be presented as a whole number (no decimal places), and values less than 1% will be presented as “<1%.” Values less than 100% but that round up from 99.5% to 100% will be presented as “>99%.”

6.3.5. Standard Calculations

Variables requiring calculation will be derived using the following formulas:

- **Days:** A duration expressed in days between one date (*date1*) and another later date (*date2*) will be calculated using the following formulas:

$$\text{duration (days)} = \text{date2} - \text{date1} + 1$$

- **Months:** A duration expressed in months is calculated as the number of days divided by 365.25 / 12.

- **Years**—A duration expressed in years between one date (*date1*) and another date (*date2*) is calculated using the following formulas:

$$\text{duration (years)} = (\text{date2} - \text{date1} + 1) / 365.25$$

- **Age**—Age is calculated as the number of years from the date of birth (*DOB*) to the specified date, eg, date of informed consent (*DOIC*). If the month of DOIC < month of DOB or the month of DOIC=DOB and the day of DOIC < day of DOB, then the following formula is used:

$$\text{age (years)} = \text{year of DOIC} - \text{year of DOB} - 1.$$

Otherwise, the following formula is used:

$$\text{age (years)} = \text{year of DOIC} - \text{year of DOB}.$$

- **Height:** Height measured in inches (in) are converted to centimeters (cm) using the following formula:

$$\text{height (cm)} = \text{height (in)} \times 2.54$$

- **Weight:** Weight measured in pounds (lb) are converted to kilograms (kg) using the following formula:

$$\text{weight (kg)} = \text{weight (lb)} / 2.2046$$

- **Temperature:** Temperature measured in degrees Fahrenheit are converted to degrees centigrade using the following formula:

$$\text{temp (degrees centigrade)} = 5 / 9 \times (\text{temp [degrees Fahrenheit]} - 32)$$

- **Body Mass Index (BMI):** BMI is calculated using height (cm) and weight (kg) using the following formula:

$$\text{BMI (kg/m}^2\text{)} = \text{weight (kg)} / ([\text{height (cm)} / 100]^2)$$

- **Change from Baseline:** Change from Baseline is calculated as:

$$\text{change from Baseline} = \text{DB post-Baseline value} - \text{Baseline value}$$

- **Percentage change from Baseline:** Percentage change from Baseline is calculated as:

$$\text{percentage change from Baseline} = 100 \times ([\text{DB post-Baseline value} - \text{Baseline value}] / \text{Baseline value})$$

- **Geometric mean** - In order to calculate a geometric mean and corresponding 95% CI, the following steps are used:

- Transform the data by taking natural logarithms (\log_e)

- Calculate the mean and 95% CI of the \log_e -transformed data
- Exponentiate the mean and the lower and upper CIs back to the original scale in order to obtain the geometric mean and corresponding 95% CI.

The geometric coefficient of variation (geometric CV%) is calculated as $100 * \sqrt{e^{SD^{**2}} - 1}$ where SD is the SD of the \log_e -transformed data.

- **Coefficient of variation** - The coefficient of variation (%) will be calculated as the ratio of the standard deviation to the arithmetic mean using the following formula:

$$\text{Coefficient of variation} = \frac{\text{standard deviation}}{\text{arithmetic mean}}$$

6.3.6. Pruritus 5-D Itch Score Calculations

The 5-D questionnaire ([Elman 2010](#)) is a specific tool used to quantify the magnitude of pruritus in PBC (and other diseases). It consists of 5 domains: duration, degree, direction, disability, distribution, as well as the total score. The following rules will be used to calculate the domain scores:

- Single item domain scores (duration, degree, and direction) are equal to the value indicated below the response choice (range from 1-5).
- The disability domain includes 4 items that assess the impact of itching on daily activities: sleep, leisure/social activities, housework/errands, and work/school. The score for the disability domain is achieved by taking the highest score on any of the 4 items. The disability domain will only be calculated if at least 3 daily activities are documented, otherwise this domain score will be set to missing.
- For the distribution domain, only the section “Mark whether itching has been present in the following parts of your body over the last 2 weeks” will be used. The distribution domain includes 16 potential locations of itch, including 15 body part items and one point of contact with clothing. Points of contact with clothing will only count as one point. Missing ticks are interpreted to be absent. The number of affected body parts (‘present’) is tallied (potential sum 0 to 16) and the sum is sorted into 5 scoring bins: sum of 0 to 2 = score of 1, sum of 3 to 5 = score of 2, sum of 6 to 10 = score of 3, sum of 11 to 13 = score of 4, sum of 14 to 16 = score of 5.
- The total 5D score is obtained by summing up the domain scores and ranges between 5 (no pruritus) and 25 (most severe pruritus). The total score will not be calculated if any of the domain scores is missing.
- If multiple answers are given for any item then the most severe one will be used.

7. ANALYSIS POPULATIONS

The following analysis populations will be used:

7.1. Intent-to-Treat (ITT) Population

All randomized subjects who receive any amount of investigational product will be included in the ITT population. Treatment assignment will be based on the randomized treatment. The ITT population will be used for the analysis of all efficacy data.

7.2. Week 12 Completer Population

The Week 12 Completer (W12C) population will include all ITT subjects who complete the DB Phase Week 12 ALP assessment and do not have a major protocol deviations that potentially affect the efficacy of the study drug. Treatment assignment will be based on the randomized treatment.

7.3. Week 24 Completer Population

The Week 24 Completer (W24C) population will include all ITT subjects who complete the DB Phase Week 24 ALP assessment and do not have a major protocol deviations that potentially affect the efficacy of the study drug. Treatment assignment will be based on the randomized treatment.

7.4. Per Protocol Population

All randomized subjects without major protocol deviations that potentially affect the efficacy of the study drug will be included in the per protocol population. Subjects who are in the study through Week 12 who do not up titrate their dose of IP will be excluded from the per protocol population. Treatment assignment will be based on the randomized treatment.

7.5. Safety Population

The Safety population will include all subjects who receive any amount of investigational product. Treatment assignment will be based on the treatment actually received. The Safety population will be used for the analysis of all safety data.

7.6. Pharmacokinetic (PK) Population

The PK Population will include all OCA subjects who consent to participate in the PK assessments and have at least one confirmed fasted analyzable sample. Subjects must have been fasting for approximately 8 hours before the visit and must not have any major protocol deviations that potentially affect exposure levels. The PK Population will be used for the OCA PK and pharmacodynamic (PD) analyses.

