5.2.6. Pharmacodynamic Bile Acids

The following are PD bile acid endpoints: total bile acids, ursodeoxycholic acid (UDCA), chenodeoxycholic acid (CDCA), lithocholate acid (LCA), cholic acid (CA), deoxycholic acid (DCA), (conjugated and unconjugated forms) and C4 in relation to the average exposure of total OCA.

- Observed values and change from Baseline will be evaluated at each DB post-Baseline visit

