9.2.4. PK and PD Concentrations

Unconjugated OCA, glyco-OCA, and tauro-OCA will be summed to create total OCA concentration. Concentrations will be converted from ng/mL units for each analyte to ng-equivalence of OCA/mL units using the following molecular weights (MW): unconjugated OCA = 420.6 g/mol, glyco-OCA = 477.7 g/mol, and tauro-OCA = 527.8 g/mol. The PK Population will be used in the analysis of PK and bile acid data (if performed). Data will be presented to 3 significant figures. The PK and PD analyses are considered exploratory analyses per the protocol.

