9.2.4.1. PK Concentrations

The values at Week 12 and Week 24 for OCA (unconjugated), glyco-OCA, tauro-OCA, total OCA, and C4 will be summarized using descriptive statistics as defined in [Section 6.2.1](#) and [Section 6.2.6](#) using both arithmetic and geometric statistics. Plasma concentration data of OCA (unconjugated), glyco-OCA, tauro-OCA, total OCA, and C4 will be listed by subject, nominal sampling time, actual sampling time, and calculated elapsed time. Standard summary statistics will be calculated for concentrations at each time point.

Mean (SD) and median plasma concentration versus time data of OCA (unconjugated), glyco-OCA, tauro-OCA, total OCA, and C4 will be plotted on a linear and semi-logarithmic scale using nominal time. Figures of linear and semi-logarithmic plots will be generated for individual subject plasma concentration versus time using the actual sampling times.

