The PK population will be used to summarize the total bile acid concentrations. The individual bile acids, total endogenous bile acids, and each of the bile acid proportions will be summarized by treatment group using descriptive statistics. Values BLQ will be treated as lower limit of quantification (LLOQ)/2. For total UDCA and total endogenous bile acid, the change from Baseline concentrations within each treatment group will be compared using a paired t-test. Only samples from subjects that have a confirmed fasting (based on eCRF) of approximately 8 hours or more prior to the subject's visit will be included in the analysis. The final determination of subjects included in the PK population and the samples included will be determined prior to database lock of the DB phase.

Reporting and Significant Figures: The concentration data as reported by the respective bioanalytical group should be used without rounding for all analysis. The non-compartmental parameters should not be reported to any greater accuracy than that of the concentration data. Default significant figures used for reporting in text and tables of the study report is three significant figures, except for time-related parameters (h) and for geometric least square mean ratios. Time-related parameters (h) will be presented with two decimal places. Geometric least square ratios will be presented with two decimal places.

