| 14.2.7 | ITT | Summary of Farnesoid X Receptor Activity by Treatment and Visit |
| 14.2.8.1 | ITT | Summary of Pruritus Visual Analogue Scale Scores by Treatment and Visit |
| 14.2.8.2 | ITT | Summary of Pruritus 5-D Itch Scores by Treatment and Visit |
| 14.2.8.3 | ITT | Summary of Partial Mayo Score by Treatment and Visit |
| 14.2.8.4 | ITT | Summary of Chron's Disease Activity Index Score by Treatment and Visit |
| 14.2.9.1 | ITT | Summary of Ulcerative Colitis Remission by Treatment and Visit |
| 14.2.9.2 | ITT | Summary of Mild Ulcerative Colitis by Treatment and Visit |
| 14.2.9.3 | ITT | Summary of Crohn's Disease Remission by Treatment and Visit |
| 14.2.10 | PK | Summary of Week 12 and 24 Plasma Concentrations for Unconjugated OCA, OCA, Glyco-OCA, Tauro-OCA, and Total OCA |
| 14.2.8 | PK | Summary of Week 12 and 24 Plasma PK Parameters for Unconjugated OCA, OCA, Glyco-OCA, Tauro-OCA, and Total OCA |
| 14.2.9.1 | PK | Summary of Total Bile Acids and Total Endogenous Bile Acids |
| 14.2.9.2 | PK | Summary of Bile Acids and Bile Acid Sub-components |
| 14.2.9.3 | PK | Summary of Bile Acid Proportions |
| 14.3 | | Safety Data |
| 14.3.1 | ITT | Summary of Investigational Product Exposure |
| 14.3.2.1 | ITT | Summary of Prior Concomitant Medications |

| | | |
|---------------|--------|--|
| 14.3.2.2 | ITT | Summary of New Concomitant Medications |
| 14.3.1 | | Displays of Adverse Events |
| 14.3.1.1 | Safety | Overall Summary of Treatment Emergent Adverse Events |
| 14.3.1.2.1 | Safety | Summary of Treatment Emergent Adverse Events by System Organ Class and Preferred Term |
| 14.3.1.2.2 | Safety | Summary of Treatment Emergent Adverse Events by Preferred Term |
| 14.3.1.3.1 | Safety | Summary of Investigational product-related Treatment Emergent Adverse Events by System Organ Class and Preferred Term |
| 14.3.1.3.2 | Safety | Summary of Investigational product-related Treatment Emergent Adverse Events by Preferred Term |
| 14.3.1.4.1 | Safety | Summary of Serious Adverse Events by System Organ Class and Preferred Term |
| 14.3.1.4.2 | Safety | Summary of Serious Adverse Events by Preferred Term |
| 14.3.1.5.1 | Safety | Summary of Treatment-Emergent Adverse Events Leading to Investigational Product Withdrawal or Study Discontinuation by System Organ Class and Preferred Term |
| 14.3.1.5.2 | Safety | Summary of Treatment-Emergent Adverse Events Leading to Investigational Product Withdrawal or Study Discontinuation by Preferred Term |

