| 14.2.3.6.2.1.2 | PK | Scatter Plot of Week 12 Change from Baseline in CA (unconjugated) versus Total OCA AUC ₀₋₆ |
| 14.2.3.6.2.2.1 | PK | Scatter Plot of Week 24 Change from Baseline in CA (conjugated) versus Total OCA AUC ₀₋₆ |
| 14.2.3.6.2.2.2 | PK | Scatter Plot of Week 24 Change from Baseline in CA (unconjugated) versus Total OCA AUC ₀₋₆ |
| 14.2.3.7.1.1.1 | PK | Scatter Plot of Week 12 DCA (conjugated) versus Total OCA AUC ₀₋₆ |
| 14.2.3.7.1.1.2 | PK | Scatter Plot of Week 12 DCA (unconjugated) versus Total OCA AUC ₀₋₆ |
| 14.2.3.7.1.2.1 | PK | Scatter Plot of Week 24 DCA (conjugated) versus Total OCA AUC ₀₋₆ |
| 14.2.3.7.1.2.2 | PK | Scatter Plot of Week 24 DCA (unconjugated) versus Total OCA AUC ₀₋₆ |
| 14.2.3.7.2.1.1 | PK | Scatter Plot of Week 12 Change from Baseline in DCA (conjugated) versus Total OCA AUC ₀₋₆ |
| 14.2.3.7.2.1.2 | PK | Scatter Plot of Week 12 Change from Baseline in DCA (unconjugated) versus Total OCA AUC ₀₋₆ |
| 14.2.3.7.2.2.1 | PK | Scatter Plot of Week 24 Change from Baseline in DCA (conjugated) versus Total OCA AUC ₀₋₆ |
| 14.2.3.7.2.2.2 | PK | Scatter Plot of Week 24 Change from Baseline in DCA (unconjugated) versus Total OCA AUC ₀₋₆ |
| 14.2.3.2.1.1 | PK | Scatter Plot of Week 12 C4 versus Total OCA AUC ₀₋₆ |
| 14.2.3.2.1.2 | PK | Scatter Plot of Week 24 C4 versus Total OCA AUC ₀₋₆ |
| 14.2.3.8.1.1 | PK | Scatter Plot of Week 12 Change from Baseline in C4 versus Total OCA AUC ₀₋₆ |
| 14.2.3.8.1.2 | PK | Scatter Plot of Week 24 Change from Baseline in C4 versus Total OCA AUC ₀₋₆ |
| 14.2.3.8.2.1 | PK | Scatter Plot of Week 12 Change from Baseline in C4 versus Total OCA AUC ₀₋₆ |
| 14.2.3.8.2.2 | PK | Scatter Plot of Week 24 Change from Baseline in C4 versus Total OCA AUC ₀₋₆ |

List of Data Listings

| Listing Number | Listing Title |
|-----------------------|--|
| 16.2 | Subject Data Listings |
| 16.2.1 | Discontinued subjects |
| 16.2.1.1 | Analysis Populations |
| 16.2.1.2 | Subject Disposition |
| 16.2.2 | Protocol deviations |
| 16.2.2.1 | Protocol Deviations |
| 16.2.2.2 | Inclusion and Exclusion Criteria Findings |
| 16.2.4 | Demographic data |
| 16.2.4.1 | Demographics and Baseline Characteristics |
| 16.2.4.2 | PSC Disease History |
| 16.2.4.3 | Medical History |
| 16.2.5 | Compliance and/or drug concentration data |
| 16.2.5.1 | Investigational Product Accountability |
| 16.2.5.2 | Investigational Product Exposure |
| 16.2.5.3 | UDCA Administration |
| 16.2.5.4 | Concomitant Medications |

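### Bile acids and C4 are summarised only in PK-consenting OCA subjects, so the randomised placebo control is not used, and C4 change from Baseline has no table

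*SAP*

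**What the plan says.** **Population.** SAP 7.6: "The PK Population will include all OCA subjects who consent to participate in the PK assessments". It also requires a confirmed fasted sample and no major deviation affecting exposure, and it assigns this set to both the PK and the PD analyses. SAP 9.2.4 applies it to bile acids: "The PK Population will be used in the analysis of PK and bile acid data (if performed"). SAP 9.2.4.3 does the same for the bile acid summaries.

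**Tests.** In SAP 9.2.4.3, for total UDCA and total endogenous bile acids only, "the change from Baseline concentrations within each treatment group will be compared using a paired t-test".

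**C4.** SAP 9.2.4.1: "The values at Week 12 and Week 24 for OCA (unconjugated), glyco-OCA, tauro-OCA, total OCA, and C4 will be summarized". SAP 9.2.4.2 adds Week 12 and Week 24 AUC0-6 and Cmax. The bile acid list in SAP 9.2.4.3 does not include C4.

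**Outputs.** Appendix A gives "Summary of Week 12 and 24 Plasma Concentrations for Unconjugated OCA, OCA, Glyco-OCA, Tauro-OCA, and Total OCA" and "Summary of Total Bile Acids and Total Endogenous Bile Acids", both labelled PK. C4 change from Baseline occurs among the figures, for example "Scatter Plot of Week 12 Change from Baseline in C4 versus Total OCA" AUC0-6, also labelled PK.

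**Aim and schedule.** SAP 2 lists the effect of OCA on PD bile acids as a secondary objective. SAP 5.2.6 defines the endpoints as the bile acids ("conjugated and unconjugated forms) and C4 in relation to the average exposure of total OCA"), with observed values and change from Baseline at each post-Baseline visit. Protocol Table 1 schedules plasma bile acids and C4 at Day 0, Week 12 and Week 24. The consent condition (footnote w) is attached to the PK row alone.

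**The concern.** An aim stated as an effect of OCA calls for a comparison with subjects who did not receive OCA. The trial has a randomised placebo arm, and the protocol schedules the same samples in it, but the SAP's choice of population removes that arm from these analytes. What remains is a before-after comparison within each OCA arm. This cannot separate a drug effect from background change over 12 or 24 weeks. FGF-19 is treated differently: SAP 9.3.1 gives it the ANCOVA, and Appendix A lists it in ITT.

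C4 has a second problem. Its change from Baseline is a stated endpoint with no tabulated result, so a reader of the report would have to take it from scatter plots drawn against exposure.

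**Working it through.** The plan gives no figure on this point to reproduce. The check compares the texts and then counts samples.

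**1. Can placebo enter any summary?** SAP 7.6 admits OCA subjects only, so the treatment-group summaries in SAP 9.2.4.3 cannot include placebo. SAP 7.1 and 9 say in general terms that efficacy analyses use ITT and the completer sets. However, the specific text in 7.6, 9.2.4 and 9.2.4.3 and the Appendix A labels all name the PK Population. The MMRM tables in Appendix A cover ALP, hepatic biochemistry and inflammation markers, not bile acids or C4.

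**2. Are the samples scheduled for everyone?** The visit lists in Protocol 8.6.4, 8.6.7 and 8.6.10 order plasma bile acids and C4 without a consent condition. The Week 12 and Week 24 lists give PK sampling as a separate item. The PK row in Table 1 has no Day 0 mark, so any Baseline value must come from the all-subject rows.

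**3. C4: promise against delivery.**
- Observed values: promised in SAP 5.2.6 and summarised in 9.2.4.1 and 9.2.4.2, but no Appendix A table title names C4.
- Change from Baseline: promised in SAP 5.2.6, not summarised in 9.2.4.1 or 9.2.4.2, and shown only in scatter plots (SAP 9.2.5, Appendix A).

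**4. Sample count.** Protocol 6.3 gives 25 subjects per group.
- Scheduled sets, before dropout: 75 × 3 = 225.
- Placebo sets: 25 × 3 = 75, and 75/225 = 33%.
- Left out at PK uptake u among the 50 OCA subjects: 225 − 50 × u × 3.

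The documents do not give u, so the lower two rows are assumptions.

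| u | Used | Left out |
|---|---|---|
| 100% | 150 | 75 (33%) |
| 70% | 105 | 120 (53%) |
| 30% | 45 | 180 (80%) |

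**5. What a within-arm test can show.** Assume a change common to all arms and no drug effect. The paired t-test at two-sided 0.05 (noncentral t, n − 1 df, noncentrality = drift in SD × √n) rejects as follows. The drift values and n are illustrative.

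| n in arm | Drift 0.2 SD | Drift 0.5 SD |
|---|---|---|
| 6 | 7% | 17% |
| 12 | 10% | 35% |
| 25 | 16% | 67% |

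**6. What a placebo comparison could show.** This uses a two-sample t-test at two-sided 0.05, with no gain from Baseline adjustment assumed. The 20 per arm is 25 × (1 − 0.20), the dropout in SAP 4. The 95% CI half-width is t(0.975, 2n − 2) × √(2/n).

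| n per arm | Difference for 80% power | 95% CI half-width |
|---|---|---|
| 25 | 0.81 SD | 0.57 SD |
| 20 | 0.91 SD | 0.64 SD |

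Missing, non-fasted or unassayed samples would make these larger.

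**The case against.** The strongest defence is that the population fits the purpose. SAP 5.2.6 frames these endpoints in relation to OCA exposure. Protocol 12.4 specifies an exposure-response assessment, and SAP 9.2.5 plots change against AUC0-6. An OCA-only set is right for that work. SAP 9.2.4 calls the PK and PD analyses exploratory, and 9.2.4 and 9.2.4.3 make bile acid analysis optional. Protocol 8.6.2 and 10.5 describe an optional PK and bile acid assessment at selected sites. Protocol Appendix A allows tests to be omitted, and Table 1 footnote t says where samples are analysed, not that placebo bile acids will be assayed. All of this stands, and it limits the weight of the point. It does not supply a control for the secondary objective. Protocol 10.5 also describes an additional assessment, which does not cancel the routine samples in Table 1.

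A reader might infer three stronger claims that the documents do not support:
- **The SAP drops a promised placebo comparison.** Protocol 12.3.2 assigns the ANCOVA to hepatic biochemistry and to fibrosis and inflammation markers. It promises none for bile acids or C4.
- **Placebo samples are entirely unused.** SAP 6.1 lists all subject data, including derived changes, and the bile acid listings in Appendix A carry no population limit. Placebo values, and C4 changes, may appear there.
- **C4 is tested within arm, or is not summarised at all.** It has no planned test, and SAP 9.2.4.1 and 9.2.4.2 do commit to summaries of its values, AUC0-6 and Cmax.

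Appendix A also has duplicated table numbers and figure titles, so the absence of C4 from its table titles may be an oversight. The missing change-from-Baseline summary in 9.2.4.1 and 9.2.4.2 does not depend on those titles.

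**Conclusion.** The point holds as an inexpensive improvement, not as a defect that threatens the trial. The restriction to PK-consenting OCA subjects is explicit, and it leaves a secondary objective with uncontrolled within-arm evidence: tests for two totals, and none for C4 or the other totals. The minimum exclusion, one third of scheduled sets, follows from the population definition and 1:1:1 allocation. Anything above that depends on PK uptake, which is not stated. The C4 gap between SAP 5.2.6 and the planned outputs stands whatever is decided about placebo.

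The benefit of a placebo comparison is limited by precision and rests on placebo samples being collected and assayed, which the documents do not guarantee. No primary, safety or confirmatory conclusion is affected.

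**What to change.** Keep the PK Population for PK parameters and exposure-response. If bile acids and C4 are analysed, make these additions:

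- Summarise change from Baseline in total endogenous bile acids, the individual bile acid totals and C4 in ITT subjects with confirmed-fasted samples.
- Compare each OCA group with placebo using the SAP 6.2.3 ANCOVA and its rank fallback. The model already contains the UDCA and bilirubin strata.
- Report total UDCA by UDCA use.
- Label the comparisons exploratory and without multiplicity control, which agrees with SAP 6.2.7.
- Add a C4 change-from-Baseline table to Appendix A, and name C4 in the concentration and PK parameter tables.

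The cost is some SAP wording and a few tables. If not already done, it also includes assay of samples already scheduled: up to 75 sets from placebo subjects, plus those from OCA subjects outside the PK Population. The sponsor should first confirm whether placebo assays exist. If they will not be run, the SAP should say so and describe the bile acid and C4 results as uncontrolled.
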